7.1.2. Nivolumab Packaging, Labeling and Storage

Nivolumab (Opdivo) is a human monoclonal antibody that blocks the interaction between PD-1 and its ligands, PD-L1 and PD-L2 (64). Nivolumab is an IgG4 kappa immunoglobulin that has a calculated molecular mass of 146 kDa.

Nivolumab (OPDIVO) is a sterile, preservative-free, non-pyrogenic, clear to opalescent, colorless to pale-yellow liquid that may contain light (few) particles. OPDIVO injection for intravenous infusion is supplied in single-use vials. Each mL of OPDIVO solution contains nivolumab 10 mg, mannitol (30 mg), pentetic acid (0.008 mg), polysorbate 80 (0.2 mg), sodium chloride (2.92 mg), sodium citrate dihydrate (5.88 mg), and Water for Injection, USP. May contain hydrochloric acid and/or sodium hydroxide to adjust pH to 6.

Nivolumab (OPDIVO) is available as 40 mg/4 ml and 100 mg/10 ml single use vials. Store nivolumab under refrigeration at 2°C to 8°C (36°F-46°F). Protect nivolumab from light by storing in the original package until time of use. Do not freeze or shake.

7.2. ABI-009 and Nivolumab Accountability, Disposal, and Compliance

For ABI-009, only completely unused study drug vials should be retained by the site until a representative from AADi or Sponsor-nominated CRO has completed an inventory. Partially used and completely used vials should be destroyed according to the site's guidelines, and their disposition should be recorded on the Investigational Drug Accountability Record Form.

For ABI-009, the Investigator, or designee, shall record the dispensing of study drug to patients and any remaining study drug after dosing in a study drug accountability record. The study drug record will be made available to AADi or authorized AADi-designated monitoring personnel for the purpose of accounting for the study drug supply. Inspections of the study drug supply for inventory purposes and assurance of proper storage will be

conducted as necessary. Any significant discrepancy will be recorded and reported to AADI or their designee and a plan for resolution will be documented.

Accurate recording of all ABI-009 administration will be made in the appropriate section of the patient's CRF and source documents. The investigator or designee is responsible for accounting for all study-specific IP either administered or in their custody during the course of the study.

For Nivolumab, the Investigator, or designee, shall record the dispensing of study drug to patients. The study drug record will be made available to AADI or authorized AADI-designated monitoring personnel for the purpose of accounting for the use of the drug.

Accurate recording of all nivolumab administration will be made in the appropriate section of the patient's CRF and source documents. The investigator or designee is responsible for accounting for all study-specific IP either administered or in their custody during the course of the study.

7.3. ABI-009 Reconstitution

NOTE: It is not a requirement to use filter needles in the preparation, or in-line filters during the administration of ABI-009. In any event, filters of pore size less than 15 microns (15 μm) must not be used.

ABI-009 will be reconstituted by appropriate study personnel and administered to the patient in the study site (see below). The Investigator will calculate the BSA of the patient in order to determine the total amount of ABI-009 to be administered.

Reconstitution and Use of ABI-009:

1. Calculate the patient's BSA according to standard institutional methods. BSA will be calculated at baseline and recalculated if the weight changes by >10%.

Calculate the total dose (in mg) to be administered by:

$$\text{Total Dose (mg)} = \text{BSA} \times (\text{study dose mg/m}^2)$$

2. Calculate the total number of vials required by:

$$\text{Total Number of Vials} = \frac{\text{Total dose (mg)}}{100 \text{ (mg/vial)}}$$

Round up the number of vials to be reconstituted to the next higher whole number when a fractional number of vials is obtained by the above formula (e.g., if the total number of vials = 4.05 or 4.5, then 5 vials would be reconstituted).

3. Using sterile technique, prepare the vials for reconstitution.
4. Swab the rubber stoppers with alcohol.
5. Reconstitute each ABI-009 vial by using a 50-cc or 60-cc sterile syringe to inject 20 mL of 0.9% Sodium Chloride Injection into each vial over a period of not less than 1 minute (Note: Change the syringes after reconstituting every 3 vials).

- Aseptically, reconstitute each vial by injecting 20 mL of 0.9% Sodium Chloride Injection.
- **Slowly** inject the 20 mL of 0.9% Sodium Chloride Injection over a minimum of 1 minute, using the sterile syringe to direct the solution flow onto the **INSIDE WALL OF THE VIAL**.
- **DO NOT INJECT** the 0.9% Sodium Chloride Injection directly onto the lyophilized cake as this will result in foaming.
- Once the injection is complete, allow the vial to sit for a **minimum of 5 minutes** to ensure proper wetting of the lyophilized cake/powder.
- **Gently** swirl and/or invert the vial **slowly** for at least **2 minutes** until complete dissolution of any cake/powder occurs. **Avoid** generation of foam.
- If foaming or clumping occurs, stand solution for at least 15 minutes until foam subsides.
- Each mL of reconstituted product will contain 5 mg of rapamycin.

6. Calculate the exact total dosing volume (to the nearest mL) of 5 mg/mL suspension required for the patient:

Dosing volume (mL) = Total dose (mg)/5 (mg/mL)

7. The reconstituted sample should be translucent and homogeneous without visible particulates. If unsuspended powder is visible, the vial should be **gently** inverted again to ensure complete resuspension, prior to use.
8. Using a new, sterile 50-cc or 60-cc syringe, withdraw the reconstituted ABI-009 solution. Do not remove the rubber stopper from the ABI-009 vials as this can compromise the sterility of the drug preparation.
9. Inject the calculated dosing volume of reconstituted ABI-009 suspension into an empty sterile, standard PVC or non-PVC IV bag using an injection port. Inject perpendicularly into the center of the injection port to avoid dislodging plastic material into the IV bag. Repeat steps 9 and 10 until the patient's entire required dose is injected into the IV bag.
10. Remove the injection port.
11. Once the exact volume of reconstituted ABI-009 has been withdrawn from the vials, discard any excess solution left over in accordance with standard operating procedures for cytotoxic drugs.
12. Administer the calculated dosing volume of reconstituted ABI-009 suspension by IV infusion over 30 minutes (+/- 10 min). The use of in-line filters is not necessary; if used, in-line filters with pore sizes of < 15 microns (15 μ m) should not be used. Upon completion of infusion, the infusion catheter should be flushed with ~2 mL normal saline to ensure all drug has been infused.

13. Reconstituted ABI-009 suspension in IV bag should be used immediately, but may be stored for up to 4 hours at 2-8°C (36°- 46°F), followed by 4 hours at room temperature (<25°C).

7.4. Receipt and Return of ABI-009

Upon receipt of the study drug supplies, the Investigator or designee will conduct an inventory and sign both copies of the study drug receipt and forward one copy to the address indicated on the form. One copy of the receipt and the packing slip must be retained in the Investigator's regulatory file records. Investigator or designee will be responsible for drug inventory, drug accountability, and disposition of unused study drug.

A representative from AADI or his/her designee will inspect the study drug inventory, Drug Accountability Record form(s), and will arrange for the disposition of any remaining unused study drug. No study drug may be returned to AADI without the representative from AADI or other AADI-designated personnel first inspecting the study drug inventory and accountability documentation.

7.5. Nivolumab (Opdivo) Reconstitution

Visually inspect drug product solution for particulate matter and discoloration prior to administration. Nivolumab is a clear to opalescent, colorless to pale-yellow solution. Discard the vial if the solution is cloudy, is discolored, or contains extraneous particulate matter other than a few translucent-to-white, proteinaceous particles. Do not shake the vial (64).

Preparation of nivolumab:

- Withdraw the required volume of nivolumab and transfer into an intravenous container.
- Dilute nivolumab with 100 ml 0.9% Sodium Chloride Injection, USP to prepare an infusion with a final concentration ranging from 1 mg/mL to 10 mg/mL.
- Mix diluted solution by gentle inversion. Do not shake.
- Discard partially used vials or empty vials of nivolumab.
 - Storage of Infusion
 - The product does not contain a preservative.

After preparation, store the nivolumab infusion either:

- at room temperature for no more than 4 hours from the time of preparation. This includes room temperature storage of the infusion in the IV container and time for administration of the infusion or
- under refrigeration at 2°C to 8°C (36°F-46°F) for no more than 24 hours from the time of infusion preparation.
- Do not freeze.

Administration of nivolumab:

- Administer the infusion over 60 minutes through an intravenous line containing a sterile, non-pyrogenic, low protein binding in-line filter (pore size of 0.2 micrometer to 1.2 micrometer).
- Do not coadminister other drugs through the same intravenous line.
- Flush the intravenous line at end of infusion.

7.6. Concomitant Medications and Procedures

Dexamethasone, 10 mg IV, will be given on D8 of every cycle, beginning Cycle 2, to preempt or reduce the incidence/severity of pneumonitis and/or hepatitis with combined use of nivolumab and ABI-009.

All concomitant treatments, including blood and blood products, must be reported on the CRF. Throughout the study, investigators may prescribe any concomitant medications or treatments deemed necessary to provide adequate supportive care except for those listed in [Section 7.8](#).

Concomitant therapies are to be collected from enrollment/randomization through the EOT Visit. Therapy name including indication, dose, frequency, route, start date and stop date will be recorded on each patient's CRF(s).

7.7. Permitted Medications and Procedures

The investigator must be informed as soon as possible about any medication taken from the time of screening until the end of the clinical phase of the study (final study visit). Any concomitant medication(s), including herbal preparations, taken during the study will be recorded in the CRF. The minimum requirement is that drug name, dose, and the dates of administration are to be recorded. Additionally, a complete list of all prior cancer therapies will be recorded in the CRF.

Patients should receive full supportive care during the study, including transfusions of blood and blood products, and treatment with antibiotics, anti-emetics, anti-diarrheas, and analgesics, and other care as deemed appropriate, and in accordance with their institutional guidelines. WBC growth factors may be administered at the discretion of the investigator, consistent with institutional guidelines.

Extreme precaution must be taken with contraceptives (either combined or progesterone only), as it is not known if there is the potential of inhibition/induction of enzymes that affect the metabolism of estrogens and/or progestins.

7.8. Prohibited Medications and Procedures

The use of certain medications, and illicit drugs within 5 half-lives or 28 days, whichever is shorter prior to the first dose of study drug and for the duration of the study will not be allowed. If a prohibited medication is required for single use (such as for a procedure) while study drug is held, the AADI medical monitor can approve such use.

The following medications or non-drug therapies are prohibited:

- Other anti-cancer therapy while on treatment in this study.
- Antiretroviral drugs (patients with known HIV are ineligible for study participation).
- Herbal remedies (eg, St. John's wort) unless approval is granted by the medical monitor.
- Rapamycin is metabolized primarily by CYP3A4. Drugs that are strong inhibitors or inducers of CYP3A4 may only be used under special circumstances (eg, as a single use for a procedure) while treatment with study drug is interrupted. The list may be modified based on emerging data.
- Use of any known CYP3A4 substrates with narrow therapeutic window (such as fentanyl, alfentanil, astemizole, cisapride, dihydroergotamine, pimozide, quinidine, terfanide) within the 14 days prior to receiving the first dose of ABI-009. Other medications may be allowed if there is agreement between the sponsor and investigator
- Use of strong inhibitors and inducers of CYP3A4 within the 14 days prior to receiving the first dose of ABI-009

8. STATISTICAL CONSIDERATIONS

8.1. Study Endpoints

Primary Endpoint:

- MTD

Secondary Endpoint(s):

- Disease control rate (DCR), ORR (CR+ PR)
- Progression-free survival
- Progression-free survival rate at 3,6,9,12 months
- Overall survival
- Incidence and grade of treatment-emergent AEs

Exploratory Endpoint(s):

- Correlation of response based on RECIST v1.1 and irRECIST
- Correlation between response and PD-L1 expression in patients' tumors
- Correlation between DCR and PTEN mutation in patient's archived tumor

8.2. Safety Analysis

Demographic and baseline information (e.g., extent of prior therapy) on study patients will be tabulated. The number of patients studied for the Phase 1 part of study could range from 12 to 18 evaluable patients, and 22-28 evaluable patients for the Phase 2 part of the study.

For the Phase 1 part of the study, the following information will be reported for adverse events observed in the study: dose level, type (organ affected or laboratory determination, such as absolute neutrophil count), severity (by NCI Common Terminology Criteria for Adverse Events (CTCAE) Version 4.03 and most extreme abnormal values for laboratory determinations) and relatedness to study treatment. For each dose the number and percentage of patients experiencing any grade 3, 4, or 5 adverse event will be reported, as well as the number and percentage of patients who experienced selected specific types of adverse events. In addition, the DLTs will be summarized by dose level and the MTD will be determined.

The following table gives the probability of dose escalation at a single dose level as a function of the true probability of DLT at that level using the cohorts of 3 design (Objective #1) (2).

Table 1. Probability of Dose Escalation

True Rate of DLT (%)	Probability of Dose Escalation
10	0.91
20	0.71
30	0.49
40	0.31
50	0.17

For the Phase 2 part of the study, the entire treated population (Full Analysis Set) will be the analysis population for all safety analyses. Adverse events will be coded using the NIH CTCAE v4.03. Summary tables will include the number and percentage of patients with AEs, serious AEs, fatal AEs and other AEs of interest. Safety will be analyzed in all patient groups together (metastatic and locally advanced). Although this study will not be large enough to allow firm conclusions about safety or efficacy, it will provide preliminary data on safety and efficacy that will be useful in planning future studies. Frequency tables, graphs, and summary statistics will be used for outcome data.

Patient incidence of all treatment-emergent AEs will be tabulated. Tables of fatal adverse events, serious adverse events, treatment-related AEs, and adverse events leading to withdrawal from investigation product will also be provided.

For select laboratory parameters, changes of laboratory values over time (e.g., change from baseline summary statistics), grade shifts in laboratory values from baseline to worst on-study value, and grade 3 or higher laboratory toxicities will be summarized.

The ECG measurements from this study will be performed as per standard of care for routine safety monitoring.

For ABI-009 and nivolumab exposure, summary statistic will be provided for total number of doses, average dose administered, and duration of each treatment.

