I. Dose Escalation Phase 1 Part of Study: The study will employ the standard “cohort of three” design (2). Three patients are treated at each dose level with expansion to six patients per cohort if DLT is observed in one of the three initially-enrolled patients at each dose level. If no DLT occurs after 2 doses, escalation to the next dose level will be permitted. The maximum tolerated dose is defined as the highest safely tolerated dose, where not more than one patient experienced DLT, with the next higher dose level having at least two patients who experienced DLT. Patients in the dose escalation study may continue treatment at their designated dose levels up to eighteen 3-week cycles or until significant disease progression or unacceptable toxicity occurs. No intra-patient dose escalation will take place.

Dose of nivolumab: 3 mg/kg IV over 30 min. q 3 weeks (Day 1 of every 21-day cycle)

Dose of ABI-009:

NB: ABI-009 will start after 2nd nivolumab dose and will be administered on D8 and D15 beginning in C2.

Escalating doses IV over 30 min for 2 of every 3 weeks:

Treatment Cycle	# Pts.	Dose Level	Dose, mg/m ²
Every 3 weeks	3-6	I	56
Every 3 weeks	3-6	II	75
Every 3 weeks	3-6	III	100

Note: DLT includes any \geq Grade 3 colitis, hepatitis, or pneumonitis, any Grade 1-2 colitis, hepatitis or pneumonitis that recurs, worsens or persists with oral steroids longer than 14 days, symptoms of adrenal crisis, any Grade 4 hematologic toxicity or any \geq Grade 3 non-hematologic toxicity. If DLT develops in more than 1 patient at Dose 56 mg/m², the dose will be de-escalated to 45 mg/m² and to 30 mg/m² if DLT develops at 45 mg/m².

II. Expansion Phase 2 Part of Study: Following dose escalation, an additional 22-28 patients will receive ABI-009 at the MTD and defined doses of nivolumab to assess overall safety and potential efficacy in a greater number of patients. Patients in the expansion phase of the study may continue treatment up to 18 3-week treatment cycles or until significant disease progression or unacceptable toxicity occurs.

The study will be conducted in compliance with International Conference on Harmonisation (ICH) Good Clinical Practices (GCPs).

Surgical Resection: After three or more treatment cycles, the principal investigator may recommend surgical debulking, complete surgical removal or a biopsy. If residual disease

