Follow-up period is the on-study time period after the EOT Visit. All patients that discontinue study drug and have not withdrawn full consent to participate in the study will continue in the follow-up phase for survival and initiation anticancer therapy. Follow up will continue approximately every 12 weeks (+/- 3 weeks), until death, withdrawal of consent, or the study closes, whichever is the earliest. This evaluation may be made by record review and/or telephone contact.

Study Treatment

Patients will receive nivolumab 3 mg/kg as IV infusion over 30 min every 3 weeks (Day 1 of every 21-day cycle), followed by escalating doses of ABI-009 30, 45, 75 mg/m² for 2 of every 3 weeks by IV infusion over 30 minutes. ABI-009 dosing will start after 2nd nivolumab dose and to be administered on Day 8 and Day 15 of every cycle beginning in Cycle 2. Patients will continue therapy until unequivocal clinical disease progression, unacceptable toxicity, or until in the opinion of the investigator the patient is no longer benefiting from therapy, or at the patient's discretion.

Overview of Key Safety Assessments

Safety and tolerability will be monitored through continuous reporting of treatment-emergent and treatment-related adverse events (AEs), AEs of special interest, laboratory abnormalities, and incidence of patients experiencing dose modifications, dose delay/dose not given, dose interruptions, and/or premature discontinuation of IP due to an AE. All AEs will be recorded by the investigator from the time the patient signs informed consent until 28 days after the last dose of IP. Adverse events will be graded by National Cancer Institute (NCI) Common Terminology Criteria for Adverse Events (CTCAE) v4.03.

Physical examination, vital signs, laboratory assessments (e.g., serum chemistry, hematology), and ECOG performance status will be monitored. All SAEs (regardless of relationship to IP) will be followed until resolution. Local laboratory analysis will be performed as per study schedule.

The MTD for ABI-009 will be determined, and will be used in the Phase 2 part of the study.

Overview of Key Efficacy Assessments

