In Trial 1, where patients were evaluated at baseline and during the trial for thyroid function, Grade 1 or 2 hypothyroidism occurred in 8% (21/268) of patients receiving nivolumab and none of the 102 patients receiving chemotherapy. The median time to onset was 2.5 months (range: 24 days-11.7 months). Seventeen of the 21 patients with hypothyroidism received levothyroxine. Fifteen of 17 patients received subsequent nivolumab dosing while continuing to receive levothyroxine.

Grade 1 or 2 hyperthyroidism occurred in 3% (8/268) of patients receiving nivolumab and 1% (1/102) of patients receiving chemotherapy. The median time to onset in nivolumab-treated patients was 1.6 months (range: 0-3.3 months). Four of five patients with Grade 1 hyperthyroidism and two of three patients with Grade 2 hyperthyroidism had documented resolution of hyperthyroidism; all three patients received medical management for Grade 2 hyperthyroidism.

- **Any other severe or Grade 3 treatment-related adverse reactions**

Other clinically significant immune-mediated adverse reactions can occur. Immune-mediated adverse reactions may occur after discontinuation of nivolumab therapy.

The following clinically significant, immune-mediated adverse reactions occurred in less than 1% of nivolumab-treated patients in Trial 1: pancreatitis, uveitis, demyelination, autoimmune neuropathy, adrenal insufficiency, and facial and abducens nerve paresis.

Across clinical trials of nivolumab administered at doses of 3 mg/kg and 10 mg/kg the following additional clinically significant, immune-mediated adverse reactions were identified: hypophysitis, diabetic ketoacidosis, hypopituitarism, Guillain-Barré syndrome, and myasthenic syndrome.

Nivolumab was discontinued for adverse reactions in 9% of patients. Twenty-six percent of patients receiving nivolumab had a drug delay for an adverse reaction. Serious adverse reactions occurred in 41% of patients receiving nivolumab. Grade 3 and 4 adverse reactions occurred in 42% of patients receiving nivolumab. The most frequent Grade 3 and 4 adverse reactions reported in 2% to less than 5% of patients receiving nivolumab were abdominal pain, hyponatremia, increased aspartate aminotransferase, and increased lipase. Other adverse events that occurred in $\geq 10\%$ of patients were rash, pruritus, cough, upper respiratory tract infection, peripheral edema, increased AST, increased alkaline phosphatase, hyponatremia, increased ALT, and hyperkalemia, with

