6. DESCRIPTION OF STUDY TREATMENTS (ABI-009/NIVO)

6.1. ABI-009/Nivolumab Dosage, Administration, and Schedule

For the Phase 1 part of study, patients will receive nivolumab 3 mg/kg as IV infusion over 60 min every 3 weeks, followed by escalating doses of ABI-009 56, 75, 100 mg/m² for 2 of every 3 weeks by IV infusion over 30 minutes. ABI-009 will start on Day 8 of Cycle 2. If DLT develops in more than 1 patient at Dose 56 mg/m², the dose will be de-escalated to 45 mg/m² and to 30 mg/m² if DLT develops at 45 mg/m². Patients will continue therapy until unequivocal clinical disease progression, unacceptable toxicity, or until in the opinion of the investigator the patient is no longer benefiting from therapy, or at the patient's discretion.

For the Phase 2 part of study, patients will receive nivolumab 3 mg/kg as IV infusion over 30 min every 3 weeks, followed by ABI-009 at the MTD dose for 2 of every 3 weeks by IV infusion over 30 minutes. ABI-009 will start on Day 8 of Cycle 2. Patients will continue therapy until unequivocal clinical disease progression, unacceptable toxicity, or until in the opinion of the investigator the patient is no longer benefiting from therapy, or at the patient's discretion.

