9.3. Evaluation of Adverse Events

The investigator must assign the following AE attributes:

- AE diagnosis or syndrome(s), if known (if not known, signs or symptoms)
- Dates of onset and resolution (if resolved)
- Severity [and/or toxicity per protocol]
- Assessment of relatedness to the IP
- Assessment of relatedness to protocol-required procedures
- Action taken

The AE toxicity grading scale used will be the NCI CTCAE Version 4.03.

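### The Phase 1 by-dose adverse-event tables count events from the 28-day nivolumab-alone lead-in under an ABI-009 dose level not yet given

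*Combined protocol and SAP*

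**What the plan says.** **By-dose tables.** For Phase 1, Section 8.2 and the matching Safety Analyses text in the synopsis list what is reported for each adverse event: dose level, type, severity and relatedness. The list ends with "most extreme abnormal values for laboratory determinations) and relatedness to study treatment". The next sentence gives the summary: "For each dose the number and percentage of patients experiencing any grade 3, 4, or 5 adverse event will be reported". Section 2.3 defines the dose levels by ABI-009 dose alone (56, 75 and 100 mg/m²); the nivolumab dose is the same at every level.

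**Timing of the two drugs.** Nivolumab is given on Day 1 of each 21-day cycle. Section 6.1 states: "ABI-009 will start on Day 8 of Cycle 2".

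**Recording window.** The synopsis (Overview of Key Safety Assessments) states: "All AEs will be recorded by the investigator from the time the patient signs informed consent". Section 9.2 repeats the start at consent, but later in the same section makes the investigator responsible for reporting events that occur after the first dose of IP. The synopsis names ABI-009 as the IP and lists nivolumab separately as the approved agent.

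**Attribution.** Section 9.3 collects "Assessment of relatedness to the IP" along with onset and resolution dates. It has no separate field for each drug.

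**Laboratory values.** Section 8.2 plans "grade shifts in laboratory values from baseline to worst on-study value" for selected parameters. It does not define baseline for this purpose and does not say that the summary is by dose level. It also tabulates treatment-emergent events without saying when that period starts.

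**The concern.** A table by ABI-009 dose should describe what happened to patients on that dose. Here each patient spends four weeks on nivolumab alone, and the table is not told to leave those weeks out. A Grade 3 event on day 10 in a patient later given 75 mg/m² goes into the 75 mg/m² row, although ABI-009 cannot have caused it. With 3 to 6 patients per level, one such event can shift the row enough to suggest or to mask a dose trend.

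Reporting relatedness does not repair this. A nivolumab-related lead-in event is correctly called related to study treatment and stays in the row. The laboratory summaries have a milder form of the same gap: with one pre-study baseline, a change that arose on nivolumab alone cannot be told from one that arose after ABI-009 was added.

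What is at stake is how well the Phase 1 safety tables can be read. The protocol says these data are meant to help plan later trials.

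**Working it through.** **1. The plan's own figure.** The only computed figures in Section 8.2 are in Table 1, the probability of escalation. With true DLT rate p, the cohort-of-three rule gives (1−p)³ + 3p(1−p)²(1−p)³. For p = 10, 20, 30, 40 and 50% this is 0.906, 0.709, 0.494, 0.309 and 0.172. Table 1 shows 0.91, 0.71, 0.49, 0.31 and 0.17. The figures agree, and the present point does not affect them.

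**2. Length of the lead-in.** Take the first nivolumab dose as day 1. Cycle 2 Day 8 is then day 21 + 8 = 29, which is 28 days later. Nivolumab doses fall on days 1 and 22, both before any ABI-009.

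**3. Which events reach the by-dose table.** Under the consent-based window, events on days 1 to 28 are on the database. Section 8.2 has no rule that removes them. For a patient who goes on to ABI-009, they are therefore counted at that patient's level. Patients who never receive ABI-009 are outside the Full Analysis Set, so where that set is used their lead-in events drop out. The synopsis applies it to Phase 1 safety; Section 8.2 names it only for Phase 2.

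**4. Illustrative size.** The documents give no 28-day rate of Grade 3 or higher events on this nivolumab schedule, so the lead-in risk q is an assumption. Section 1.3.3 offers one anchor: "Grade 3 and 4 adverse reactions occurred in 42% of patients receiving nivolumab", with a median exposure of 5.3 months. At a constant hazard, and with 5.3 × 30.4375 ≈ 161 days, q = 1 − (1 − 0.42)^(28/161) ≈ 0.09. I use a range of 2% to 15% around it.

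The chance of at least one lead-in event among n patients is 1 − (1 − q)ⁿ. If a fraction t of patients have a Grade 3 or higher event on ABI-009, and the two periods are taken as independent, the table shows 1 − (1 − t)(1 − q).

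| Assumed q | At least one, n = 3 | At least one, n = 6 | t = 20% is tabulated as |
|---|---|---|---|
| 2% | 6% | 11% | 22% |
| 9% | 25% | 43% | 27% |
| 15% | 39% | 62% | 32% |

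One lead-in event raises a level's percentage by 1/3 = 33 points or 1/6 = 17 points, unless the same patient also has a later Grade 3 or higher event.

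**5. Where in the range.** The constant hazard is probably too high for immune-mediated events. Section 1.3.3 gives median onset of 2.2 months for pneumonitis (earliest 25 days) and 2.5 months for colitis (earliest 1 month), 86 to 113 days for hepatitis, and 3.5 and 6 months for nephritis. The 42% also comes from melanoma patients dosed every 2 weeks. A patient with a severe lead-in event may never reach ABI-009, which lowers q further among those tabulated. Against this, the by-dose table counts events of any cause. On balance the lower part of the range is more plausible.

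**The case against.** The strongest reply is that the table does no harm where it counts. The Phase 2 dose is the MTD, defined by the number of patients with DLT, and DLTs by dose level are a separate output. That stands. A reader might infer that lead-in events in this table distort the dose taken forward; the documents give the table no such role.

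Three other strong readings also fail:

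- A reader might infer that laboratory shifts are tabulated by ABI-009 dose from a single baseline. Section 8.2 says neither.
- A reader might infer that lead-in events are declared toxicity of the dose. The table counts events of any cause; the exact statement is that they are counted under that dose.
- A reader might infer that the problem runs through the whole trial. By-dose reporting is stated for Phase 1 only, and Phase 2 is planned at one dose.

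It can also be said that the sequential regimen is itself the treatment, so whole-regimen counts are legitimate. They are, and they should stay, but they do not compare ABI-009 dose levels well. Nor would a split isolate the effect of ABI-009, because late nivolumab events would still fall after its start. That is also true: the split removes only events that ABI-009 cannot have caused.

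Finally, if IP means ABI-009 alone, the second window in Section 9.2 would exclude lead-in events altogether. That shows that the text has two readings, not that the problem is solved.

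The descriptive aim of the study is no answer, since description by dose is the purpose of these tables.

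**Conclusion.** The point holds for the Phase 1 adverse-event tables by dose. Under the consent-based window, and with no split in Section 8.2, events from the 28 nivolumab-alone days are counted under an ABI-009 level not yet given, for patients who later receive ABI-009. The length of the lead-in and the absence of a split follow directly from the text.

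The size does not. The 6% to 39% and 11% to 62% chances rest on an assumed 2% to 15% lead-in risk, equal across patients and independent between them, and the protocol's onset data point to the low end. The consequence is noise in small cohorts and a weaker description of safety by dose, with no effect on the MTD. The change is worth making because it is cheap and alters figures that will be reported, but nothing in the dose-finding rule depends on it.

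**What to change.** In Section 8.2 and the matching synopsis text:

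1. In the Phase 1 by-dose tables, count events that start or worsen in grade on or after the first ABI-009 dose.
2. Show lead-in events, from the first nivolumab dose to before the first ABI-009 dose, in a separate table pooled over dose levels. Keep the whole-study tables.
3. For laboratory change and grade-shift summaries, add a second baseline: the last value before the first ABI-009 dose.
4. Define treatment-emergent to match these periods.
5. Reconcile the two adverse-event windows, from consent (synopsis, Section 9.2) and after the first dose of IP (later in Section 9.2). The lead-in table needs a window that covers the nivolumab-alone period.

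The cost is wording and a few more tables. Onset dates are collected (Section 9.3), and worsening of an existing condition already counts as an adverse event (Section 9.2). Chemistry and blood counts are scheduled on Day 8 (Table 2, Section 5.2.2), with assessments done before dosing (Section 5.2). No new visits, data or patients are needed.

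The before/after contrast should be labelled descriptive. The periods differ in length, nivolumab exposure accumulates, and dexamethasone also starts in Cycle 2 (Section 7.6).
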